18.5 Lupus QoL

The Lupus QoL is a lupus-specific health related QoL questionnaire consisting of 34 items grouped in 8 domains as shown below:

Table 46: Lupus Scoring

Domain	Number of items	Item numbers
Physical Health	8	1-8
Pain	3	9-11
Planning	3	12-14
Intimate Relationship	2	15, 16
Burden to Others	3	17-19
Emotional Health	6	20-25
Body Image	5	26-30
Fatigue	4	31-34

Subjects indicate their responses on a 5-point Likert response format, where 4=never, 3=occasionally, 2= a good bit of the time, 1=most of the time, and 0=all of the time (data received from the external vendor will be transformed to match this scale). Summary scores can be calculated for all 8 domains. First, the mean raw domain score must be calculated by adding up the item response scores for each domain and dividing this total by the number of items in that domain. Then, the transformed domain scores are calculated by dividing by 4 and multiplying by 100 each mean raw domain score. Transformed scores range from 0 (worst HRQoL) to 100 (best HRQoL).

Transformed domain scores can be obtained when at least 50% of the items are answered. The mean raw domain score is then calculated by totaling the item response scores of the answered items and dividing by the number of answered items. A non-applicable response is treated as unanswered and the domain score calculated as above.

Example:

Let's consider a subject who has answered the questionnaire according to [Table 47](#).

Table 47: Lupus – Example

Domain	Item #	Item Description	Response
Physical health	1	I need help to do heavy physical jobs such as digging the garden, painting and/or decorating, moving furniture	3
	2	I need help to do moderate physical jobs, such as vacuuming, ironing, shopping, cleaning the bathroom	2
	3	I need help to do light physical jobs, such as cooking/preparing meals, opening jars, dusting, combing my hair or attending to personal hygiene	3
	4	I am unable to perform everyday tasks, such as my job, childcare, housework as well as I would like to	3
	5	I have difficulty in climbing stairs	2
	6	I have lost some independence and am reliant on others	1
	7	I have to do things at a slower pace	1
	8	My sleep pattern is disturbed	4
Pain	9	I am prevented from performing activities the way I would like to because of pain due to lupus	3
	10	The pain I experience interferes with the quality of my sleep	3
	11	The pain due to my lupus is so severe that it limits my mobility	2
Planning	12	I avoid planning to attend events in the future	1
	13	Because of the unpredictability of my lupus, I am unable to organize my life efficiently	2
	14	My lupus varies from day to day, which makes it difficult for me to commit myself to social arrangements	2
Intimate relationship	15	Because of the pain I experience due to lupus, I am less interested in a sexual relationship	1
	16	I am not interested in sex	0
Burden to others	17	I am concerned that my lupus is stressful for those who are close to me	3
	18	I am concerned that I cause worry to those who are close to me	3
	19	I feel that I am a burden to my friends and/or family	3
Emotional health	20	I have found my lupus makes me resentful	3
	21	I have found my lupus makes me so fed up nothing can cheer me up	3
	22	I have found my lupus makes me sad	4
	23	I have found my lupus makes me anxious	2
	24	I have found my lupus makes me worried	2
	25	I have found my lupus makes me lacking in self-confidence	2
Body image	26	My physical appearance due to lupus interferes with my enjoyment of life	2
	27	My appearance (e.g. rash, weight gain/loss) makes me avoid social situations	2
	28	Lupus-related skin rashes make me feel less attractive	2
	29	The hair loss I have experienced makes me feel less attractive	2
	30	The weight gain I have experienced during treatment makes me feel less attractive	2
Fatigue	31	I cannot concentrate for long periods of time	2
	32	I feel worn out and sluggish	1
	33	I need to have early nights	3
	34	I am often exhausted in the morning	2

Domain Scores are provided in [Table 48](#).

Table 48: LupusQoL – Example – Domain Scores

Item	Mean Score	Transformed Mean Score
Physical health	$19/8 = 2.375$	$100 \times 2.375 / 4 = 59.4$
Pain	$8/3 = 2.667$	$100 \times 2.667 / 4 = 66.7$
Planning	$5/3 = 1.667$	$100 \times 1.667 / 4 = 41.7$
Intimate relationship	$1/2 = 0.5$	$100 \times 0.5 / 4 = 12.5$
Burden to others	$9/3 = 3$	$100 \times 3 / 4 = 75$
Emotional health	$16/6 = 2.667$	$100 \times 2.667 / 4 = 66.7$
Body image	$10/5 = 2$	$100 \times 2 / 4 = 50$
Fatigue	$8/4 = 2$	$100 \times 2 / 4 = 50$

18.6 PGIC

The PGIC is a self-rated scale that asks the subject to describe the change in activity limitations, symptoms, emotions, and overall quality of life (QoL) related to the subject's painful condition on the following scale: 1 (very much improved), 2 (much improved), 3 (minimally improved), 4 (no change), 5 (minimally worse), 6 (much worse) and 7 (very much worse). The subject will select the number that matches the subject's degree of change since beginning the treatment with evobrutinib (Hurst 2004).

The PGIC can be used as an anchor based method to assess clinically important change in which the judgment of meaningful change is made by the subject (Amirfeyz 2009).

18.7 EQ-5D-5L

The EQ-5D questionnaire comprises 5 questions (items) relating to current problems in the dimensions mobility, self-care, usual activities, pain/discomfort, and anxiety/depression. Responses in each dimension are divided into 5 ordinal levels coded (1) no problems, (2) slight problems, (3) moderate problems, (4) severe problems, (5) extreme problems. This part, called the EQ-5D descriptive system, provides a 5-dimensional description of health status.

A unique health state is defined by combining one level from each of the 5 dimensions. A total of 3125 possible health states is defined in this way. Each state is referred to in terms of a 5-digits code. For example, state 1111 indicates no problems on any of the 5 dimensions, while state 12345 indicates no problems with mobility, slight problems with self-care, moderate problems with doing usual activities, severe pain or discomfort, and extreme anxiety or depression.

The EQ-5D-5L descriptive system is followed by a VAS (EQ VAS), similar to a thermometer, ranging from 0 (worst imaginable health state) to 100 (best imaginable health state). The EQ VAS records the respondent's self-rated valuation of health state, i.e., a value which is based on the respondent's preferences (EQ VAS score). With respect to psychometric properties, the EQ VAS showed acceptable validity and reliability in subject with SLE.

Based on the EQ-5D-5L, the numeric EQ-5D-5L index can be derived, using validated translations provided by EuroQoL presented in the following XLS file. The EQ-5D-5L index is frequently used in economic evaluations: it represents societal preference values for the full set of EQ-5D-5L health states with the best state (perfect health) and "death" being assigned values of 1 and 0, respectively.

The UK country specific value set will be used in deriving the index value for all subjects.

This questionnaire will be used in the countries for which validated translations are available.

EQ-5D-5L_Crosswalk_
Index_Value_Calculato

18.8 Corticosteroid usage over time

18.8.1.1 General rules

To perform derivations with regards to CS endpoints, the following rules will be applied:

- CS will be medications with an ATC code which begins with “H02A” (CORTICOSTEROID FOR SYSTEMIC USE, PLAIN).
- All routes are considered except ophthalmic, topical, nasal and respiratory (inhalation).
- CS medications that started on or after end of treatment will not be taken into account in the analysis.
- When dose per administration or dosing frequency is missing or uninterpretable, the corresponding CS will not be included in endpoint derivation but will be listed instead. The reason why this CS is not considered in endpoint derivation will be provided in this listing. An exception is when the start and stop dates occur the same day, no dosing frequency is applicable: these administrations will be included in calculations (daily dosing frequency will be assumed as equal to 1).

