14.3.1 Disease Activity Endpoints

The following secondary endpoints to be analyzed on mITT analysis set are summarized in [Table 19](#). LLDAS is defined in [Appendix 18.1.7](#).

For SRI-4 and SRI-6 response endpoints as well as LDA status and LLDAS, the primary analysis method applied to the two-primary endpoints ([Section 14.1.2.1](#)) will be performed.

In addition, for LDA and LLDAS endpoints in [Table 19](#), the number and percentage of subjects with response or non-response will be summarized over time (by visit), using similar imputation rules as applied for the Week 52 timepoint.

Table 19 : Disease Activity Endpoints

Endpoint	Analysis method	Data Handling Notes

 • SRI-6 response at Week 52, in the serologically active subgroup • SRI-4 Response at Week 52 with a Sustained Reduction of OCS Dose to 7.5 milligrams prednisone-equivalent per day or less (≤ 7.5 mg/day) and less than or equal to (\leq) Day 1 dose during Week 41 Through Week 52, in all subjects • SRI-6 Response at Week 52 with a Sustained Reduction of OCS Dose to 7.5 milligrams prednisone equivalent per day or less (≤ 7.5 mg/day) and less than or equal to (\leq) Day 1 dose during Week 41 Through Week 52, in the HDA subgroup • SRI-4 Response at Week 52 with a Sustained Reduction of OCS Dose to 7.5 milligrams prednisone equivalent per day or less (≤ 7.5 mg/day) and less than or equal to (\leq) Day 1 dose during Week 41 Through Week 52, in the serologically active subgroup 	Same as the Primary Method in Table 17	Same as the Primary Method in Table 17

 • LDA status, defined by SLEDAI-2K ≤ 2 at Week 52 • LDA, defined by clinical SLEDAI-2K (SLEDAI-2K excluding anti-dsDNA and low complement parameters) ≤ 2 at Week 52 • LLDAS at Week 52 	Same as the Primary Method in Table 17	Same as the Primary Method in Table 17

In order to determine whether the subject had a sustained reduction of OCS Dose to ≤ 7.5 mg/day and \leq Day 1 dose during Week 41 Through Week 52, the daily dose of CS will be calculated for each analysis visit from Week 41 to Week 52, according to Appendix 18.8. If the condition is met for all days during this period, the subject will be considered as having a sustained reduction of OCS Dose.

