14.3.5 Corticosteroid usage over time

CS usage over time will be analyzed on the mITT set using data collected in “Relevant Previous Medications Details” and “Concomitant Medications” eCRF Forms.

Only CS taken at baseline or after will be taken into account. Any CS with an end date before screening date will not be taken into account in the following analysis.

General rules, missing data handling, conversions and cumulative dose is defined in Appendix 18.8.

The following endpoints will be described for statistical analysis:

- Clinically meaningful reduction in CS dose from Baseline, defined by:
 - A reduction of daily prednisone-equivalent CS dose $\geq 25\%$ to a dose of ≤ 7.5 mg/day by Week 40 + 1 day (i.e. Week 41) and sustained through Week 52

AND

- No new BILAG A organ domain scores and no more than one new BILAG B organ domain score during Weeks 40 + 1 day (i.e. Week 41) through 52.

Subjects withdrawing from treatment before Week 40 or with missing data at Week 40 will be considered as non-responders. The analysis will be performed on the mITT subjects whose CS dose is greater than or equal to 7.5 mg at baseline.

- Change from Baseline to Week 52 in prednisone-equivalent CS daily dose.

Summary statistics for absolute value, CFB and percent CFB by visit during treatment period in prednisone-equivalent CS daily dose will be provided.

- Reduction by visit, from Baseline to Week 52, in prednisone-equivalent CS daily dose of zero to < 25%, 25% to 50%, > 50%, or an increase.

The same table will be produced with the following categories of prednisone-equivalent CS daily dose at Week 52: ≤ 6 mg, > 6 - 7.5 mg, > 7.5 – 10 mg, > 10 – 20 mg, > 20 – 30 mg and > 30 mg. The proportions are based on the observed subjects as the denominator.

- Cumulative prednisone-equivalent CS dose from Baseline until completion of the Treatment Period (absolute value only) will be described using summary statistics.

Cumulative prednisone-equivalent CS dose will be compared between placebo arm and evobrutinib arms with a pairwise non-parametric Wilcoxon rank sum test.

[figure not shown]
All CS doses will be listed for each subject and flagged for any doses not taken into account in calculation of the scheduled-visit dose (e.g. dose taken between two scheduled visits or dose with missing information). Subjects non-compliant with protocol rules on CS usage will be listed based on protocol deviation data (i.e. all subjects with PD code = PDEV52e).

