18.8.1.4 Corticosteroid usage, cumulative and average daily dose

The study protocol defines rules of CS usage during the study. The non-compliance with these rules will be described using data collected in “Concomitant Medications” eCRF form and

subjects' compliance with CS usage rules checked during the medical review and protocol deviation process (i.e. subjects with PD code = PDEV52e).

According to protocol secondary criterion the following criteria will be summarized:

- Cumulative prednisone-equivalent dose (mg) from baseline visit until end of 52-week treatment period. If one subject does not receive any CS between baseline and end of treatment period then his cumulative dose will be set to 0 mg.

Cumulative dose [mg] = sum of (dose per administration * daily dosing frequency * Duration),

with:

- Sum of () = sum of all CS recorded in Concomitant Medication eCRF form, from baseline visit until the end of 52-week treatment period
- Duration = End CS dose date during treatment period – Start CS dose date + 1
- Daily dosing frequency using frequency conversions (See [Table 49](#) and [Table 50](#)).

As CS usage has to be restricted to the period between screening visit and end of treatment period, the following specific rules will be applied only for the calculation of cumulative prednisone-equivalent dose:

- Start CS dose date:
 - If start dose date is before screening date, baseline visit date will be considered as the start date for duration calculation.
 - If start dose date is after end of treatment period, CS will not be considered for duration calculation.
- End CS dose date:
 - If end is missing or after date of last IMP dose + 14 days or CS ongoing, the end CS dose date will be imputed by the last IMP dose date + 14 days for duration calculation. If last IMP dose is missing then end dose date will not be imputed and duration will not be calculated (patient not treated not taken into account in the analysis).
 - If end CS dose date is before baseline date, CS will not be considered
- Average daily steroid dose (mg) from baseline visit until end of treatment period. If one subject does not receive any CS between screening and end of treatment period then his average daily dose will be set to 0 mg.
 - Average daily dose [mg] = $\left(\frac{\text{Cumulative dose [mg]}}{\text{Duration}} \right)$
 - For completers, Duration = Week 52 date – baseline visit date + 1

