 - For discontinuers, Duration = Last IMP dose date + 14 – baseline visit date + 1

- If one subject does not receive any CS between baseline and end of treatment period then his daily dose will be set to 0 mg and change from screening value will be equal to 0 mg.
- Prednisone-equivalent daily dose [mg] by visit:
 - The prednisone-equivalent daily dose at visit X is calculated only if visit X is performed during treatment period (date of visit X \leq last treatment intake + 14 days).
 - At a scheduled visit, prednisone-equivalent CS daily dose is equal to the dose the subject is on at the scheduled visit. If several CS are taken at the same scheduled visit then all CS doses should be added. If a prednisone-equivalent CS dose stopped/changed at the scheduled visit date (Week X visit date), then the prednisone-equivalent CS dose started before (Week X visit date - 1 day) will be considered as the CS daily dose for that visit.
 - CS dose taken between two scheduled visits will not be taken into account in calculation of the scheduled-visit dose.
 - For subjects who completed the treatment period, CS dose that started on or after end of treatment will be excluded from the calculation.
 - All comparisons will be done compared to CS dosing at baseline. CS dosing at baseline is defined at CS dose taken the day of baseline visit (day 1). If patient did not receive any CS at baseline then CS dose is set to 0 mg.
 - For defining CS sparing effect endpoint (i.e. sustained reduction by W41 to Week 52), the derivation of prednisone-equivalent CS daily dose will be repeated at Week 40 scheduled visit using a different rule. If a prednisone-equivalent CS dose stopped/changed at the Week 40 scheduled visit date (Week 40 visit date), then the prednisone-equivalent CS dose started after (Week 40 visit date + 1 day) will be considered as the CS daily dose for that visit. Sustained reduction by Week 41 will be then programmed by checking that CS reduction is maintained between this new post-Week 40 (=Week 41) visit and Week 52 visit (i.e. CS dose at Week 52 is less or equal than CS dose at Week 41). The associated conditions related to CS sustained reduction (i.e. CS dose \leq 7.5 mg/day and \leq Day 1 CS dose, CS dose reduction from baseline \geq 25% and CS dose \leq 7.5 mg/day) will be checked for Week 41, 44, 48 and 52 visits.

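### Unquantified steroid records are dropped and the rest summed, so the steroid condition of several secondary endpoints can be met when the true dose is unknown

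*SAP*

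**What the plan says.** Section 18.8.1.1 of the SAP sets the general rule: "When dose per administration or dosing frequency is missing or uninterpretable, the corresponding CS will not be included in endpoint derivation". The record is listed with the reason for its exclusion. The one exception is a record that starts and stops on the same day, for which "daily dosing frequency will be assumed as equal to 1". The last paragraph of 14.3.5 agrees: doses with missing information are flagged in a listing as not used in the scheduled-visit dose.

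Section 18.8.1.4 builds the visit dose by addition: "If several CS are taken at the same scheduled visit then all CS doses should be added". Its zero defaults are conditional on no steroid having been received. At baseline, "If patient did not receive any CS at baseline then CS dose is set to 0 mg"; for the cumulative total, "If one subject does not receive any CS between baseline and end of treatment period then his cumulative dose will be set to 0 mg".

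The derived dose is used in these places:
- Section 14.3.1 (Table 19) takes it from Appendix 18.8 for three endpoints that combine SRI response with a sustained OCS reduction. The conditions are at most 7.5 mg/day and no more than the Day 1 dose, and 18.8.1.4 checks them at Weeks 41, 44, 48 and 52. Table 19 gives the data handling as "Same as the Primary Method in Table 17", where a missing Week 52 response is a non-response.
- Section 14.3.5 uses it for clinically meaningful CS reduction (at least 25%, to at most 7.5 mg/day), change in dose, dose categories and cumulative dose. For the first of these, subjects who withdraw before Week 40 "or with missing data at Week 40 will be considered as non-responders".
- Section 18.1.7 tests LLDAS at 7.5 mg/day or less, citing Tables 49 and 50.

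**The concern.** A steroid record without a usable dose or frequency shows that the subject was on a systemic steroid and that the amount is unknown. Dropping the record and summing the rest treats that unknown amount as nothing. The missing dose never surfaces as missing, so the plan's own missing-data rules have nothing to act on.

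The errors favour response after baseline. An understated visit dose makes it easier to be at or below 7.5 mg/day, at or below the Day 1 dose, and at least 25% below baseline. Post-baseline dose change shifts towards reduction, and cumulative dose, which is compared between arms by a Wilcoxon test, is understated. Section 18.8.1.2 takes the cautious line with dates: a CS record with an unknown end date that is not marked ongoing is extended to the end of 2099, so the subject stays on steroid. Unknown doses get the opposite treatment.

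At stake are binary secondary endpoints meant to show steroid sparing, where a subject could be credited with a reduction nobody observed.

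**Working it through.** The plan states no figure on this point that could be reproduced. The check follows the rule through the dose formula in constructed cases.

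**Inputs.** Prednisone factor 1 and methylprednisolone factor 1.25 (Table 49). Frequency factors QD 1, BID 2, QOD 1/2, TIW 3/7, QW 1/7 (Table 50). Thresholds from 14.3.1, 14.3.5 and 18.8.1.4. Assumed for illustration: Day 1 prednisone 10 mg QD, and the later records unchanged from Week 41 to Week 52.

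**Formula.** Visit dose D = sum over included records of (dose × prednisone factor × frequency factor). With Day 1 dose D1 = 10, the steroid conditions are D ≤ 7.5, D ≤ D1 and (D1 − D)/D1 ≥ 25%.

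**Case A: sole record dropped.** Later record: prednisone 15 mg, frequency missing.
- By summation under the plan: D = 0, reduction (10 − 0)/10 = 100%, all conditions met.
- If the record were kept: D = 15 × frequency factor.

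**Case B: partial sum.** Later records: prednisone 5 mg QD, and methylprednisolone 8 mg with frequency missing.
- Under the plan: D = 5, reduction (10 − 5)/10 = 50%, all conditions met.
- If the record were kept: D = 5 + 8 × 1.25 × frequency factor = 5 + 10 × frequency factor.

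| True frequency | Case A, mg/day | Conditions met? | Case B, mg/day | Conditions met? |
|---|---|---|---|---|
| BID | 30 | no | 25 | no |
| QD | 15 | no | 15 | no |
| QOD | 7.5 | yes | 10 | no |
| TIW | 6.43 | yes | 9.29 | no |
| QW | 2.14 | yes | 6.43 | yes |
| Plan as written | 0 (by summation) | yes | 5 | yes |

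The plan scores success in every row, while the true status depends on the unrecorded frequency. Case B needs no assumption about defaults: a quantifiable record exists, so the sum is defined, and it is too low.

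**Case C: Day 1 record dropped.** If summation gives D1 = 0, a later 5 mg/day fails the Day 1 comparison (5 ≤ 0 is false), and the subject leaves the subset with a baseline dose of at least 7.5 mg in 14.3.5. Here the error works against response. Setting D1 to missing leaves that outcome the same; it changes the steroid condition only where the later dose is also 0 mg (0 ≤ 0 is true). It would also stop an artificial increase from entering the change-from-baseline summary.

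**Safeguards in the text.** The Week 40 rule in 14.3.5 covers one endpoint at one visit and does not say whether a dropped record counts as missing data. Nothing sets a visit dose to missing, or a subject to non-responder, because a record was dropped.

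**The case against.** The best counter-argument is that the plan never assigns 0 mg to a subject whose only record is dropped. Both zero defaults apply to subjects who received no CS, and a subject with an unquantified record did receive some. Table 12 also lists a missing category for baseline CS dose apart from 0 mg/day, so a missing dose is contemplated. This stands: a reader might infer that 0 mg is the stated rule, but for a sole dropped record it follows only from omission plus summation. It does not answer the partial-sum case.

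A reader might also infer a contradiction with Table 17. The documents do not go that far. Table 17 concerns a missing response at Week 52 and 18.8.1.1 concerns individual medication records; the drop rule bypasses the non-responder rule.

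Nor do the documents support saying that rescue or tapering courses are the records most often incomplete. Courses between visits are ignored even when fully recorded (18.8.1.4). EAC-determined treatment failure is not made to depend on the Appendix 18.8 dose, so prohibited steroid use can still produce non-response.

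For LLDAS, 18.1.7 cites only Tables 49 and 50. That 18.8.1.1 applies there is a reasonable inference, since no other dose derivation is given.

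Finally, these are secondary endpoints outside the testing hierarchy with nominal p-values (14.3), the rule is the same in every arm, and excluded records are listed. That limits the consequences and leaves the derivation biased.

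**Conclusion.** The concern holds in this form. A stated rule understates the visit dose whenever an unquantified systemic CS record sits beside a quantifiable one, and leaves the value undefined, with 0 mg/day as the natural programming result, when it is the only record. The steroid condition of the three SRI plus OCS-reduction endpoints and of clinically meaningful CS reduction, and by inference LLDAS, can then be met on an unknown dose.

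For an affected subject the steroid condition can flip from not met to met. That alone does not make a responder: SRI, the BILAG conditions, the other LLDAS items and absence of EAC-treatment failure are still required where they apply. The trial-level effect is unknown because the SAP does not say how many records are affected. A reader might attach a range such as 1 to 5 percentage points; that would rest on an assumed 1 to 5% of subjects affected, all of them flipping, and nothing in the document supports either assumption. The two-primary and key secondary endpoints do not use this derivation.

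**What to change.** In 18.8.1.1 and 18.8.1.4, state that when a systemic CS record with missing or uninterpretable dose or frequency covers a visit, including Day 1, the prednisone-equivalent daily dose at that visit is missing and is not the sum of the remaining records. Keep the same-day exception. For the binary endpoints, count the subject as not meeting the steroid condition at that visit. Assign 0 mg only when no systemic CS record covers the date. State in 18.1.7 that LLDAS uses the same derivation.

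Apply the rule to the CS-dose and LLDAS summaries still planned for the LTE (14.6, Table 25), respecting the provision there that efficacy assessments missing after 23 March 2020 are not imputed. The primary analysis has already been reviewed (6.3, 6.4), so for its endpoints run this as a labelled sensitivity analysis. Cumulative dose stays a lower bound for these subjects; a footnote giving their number per arm would say so.

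The cost is a few sentences and one derivation flag, built on the exclusion listing already required. The downside is a few more missing doses and non-responders, some of whom will in truth have been on a low dose.
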